10.3. Treatment of Missing and Spurious Data

See general definitions in chapter 5.4.

10.4. Exclusion of Particular Information

See general definitions in chapter 5.5.

10.5. Descriptive Analyses

See general definitions in chapter 5.1.

10.6. Hypotheses & Statistical Tests

There are no pre-defined statistical hypotheses.

11. PHD Data: Ilivia

11.1. Analysis set

All analyses are performed for the Ilivia analysis set⁵⁴.

11.2. Variables

PHD / General data

Data file, identifier patient_display_id_full	Descriptive	Variable name	Variable label, NEW prefix added to all labels "PHD data:"	Variable level	Nominal values
phd_general_data	No	phd_visdate	Date of follow-up	date	n.a.
phd_general_data	Yes	phd_not_done	visit not performed	nominal	True / False

The following variables are analyzed as defined for the Ilivia analysis set, as described in chapter 10.2 device data.

PHD Device Data / RA

PHD Device Data / RA / Not-measured

PHD Device Data / RV

PHD Device Data / RV / Not-measured

PHD Device Data / LV / 7 Sensing Vectors

PHD Device Data / LV / 7 Sensing Vectors / Not-measured

PHD Device Data / LV / Programmed Pacing Vectors

PHD Device Data / LV / Programmed Pacing Vectors / Not-measured

Note: all variable names have the prefix "phd_" instead of "imp_".

For the programmed first and second LV pacing vector here the pacing threshold should have been measured at pulse width 0.4 ms (phd_lv_first_thresh_04 and phd_lv_sec_thresh_04, "Pacing threshold [V] at Pulse width 0.4 ms").

As threshold measurements at other pulse durations than 0.4 will be discarded (see 10.2), the variables "Pacing threshold [V]" (phd_lv_first_thresh and phd_lv_sec_thresh) and "at Pulse width [ms]" (phd_lv_first_pulse and phd_lv_sec_pulse) are not needed for analysis.

However, phd_lv_first_thresh_no and phd_lv_sec_thresh_no have the additional option "Not measured at 0.4 ms".

⁵⁴ analysis_set_Ilivia_SAR = Yes

PHD / Device Data / LV / Vector Change

Data file, identifier patient_display_id_full	Descriptive	Variable name	Variable label, NEW prefix added to all labels "PHD data: "	Variable level	Nominal values
phd_device_data	Yes	phd_lv_change	Has any of the LV vectors been changed since implant	nominal	No Yes, first LV vector Yes, second LV vector Yes, both vectors
phd_device_data	Yes	phd_lv_change_reason	Primary reason for change	nominal	Phrenic nerve stimulation High LV pacing threshold PNS and high threshold better safety margin [...] CRT optimization [...] Other
phd_device_data	Reporting for each patient if the above variable = other	phd_lv_change_reason_co	[NEW] PHD data: Comments related to Primary reason for change	text	...
phd_device_data	Yes	phd_lv_change_pns	Phrenic nerve stimulation or high pacing threshold could successfully be resolved	nominal	Yes / No
phd_device_data	Yes	phd_lv_change_pns_outcome	[New] Actions to resolve PNS	nominal	LV lead deactivated Surgical repositioning No action taken Other
phd_device_data	Reporting for each patient if the above variable = other	phd_lv_change_pns_co	[NEW] PHD data: Comments related to actions to resolve PNS	text	...

PHD Device Data / LV Programmed Delay

Data file, identifier patient_display_id_full	Descriptive	Variable name	Variable label, NEW prefix added to all labels "PHD data: "	Variable level	Nominal values
phd_device_data	Yes	phd_lvlv_reprog	LV-LV delay reprogrammed since implant	nominal	Yes / No
phd_device_data	Yes	phd_rvlv_reprog	RV-LV delay reprogrammed since implant	nominal	Yes / No
phd_device_data	Yes	phd_order_reprog	Pacing order reprogrammed since implant	nominal	Yes / No
phd_device_data	No	phd_order_rvlv	Pacing order	nominal	RV first LV first
phd_device_data	Yes, for the above groups "RV first" and "LV first"	phd_lvlv_delay	LV-LV delay [ms]	scale	n.a.
phd_device_data	Yes, for the above groups "RV first" and "LV first"	phd_rvlv_delay	RV-LV delay [ms]	scale	n.a.

PHD Device Data / CRT / Atrial burden

Data file, identifier_patient_display_id_full	Descriptive	Variable name	Variable label, NEW prefix added to all labels "PHD data: "	Variable level	Nominal values
phd_device_data	Yes	phd_crt	CRT pacing [%]	scale	n.a.
phd_device_data	Yes	phd_aburden	Atrial burden [%]	scale	n.a.

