8.5.11 Lead measurements at each follow-up

The system performance and right ventricular lead performance is evaluated at the end of the implantation procedure and **at the end** of each follow-up for both groups **A** and **B** by either manually or automatically triggered lead measurements. For this purpose the investigator performs the threshold tests, determines pacing impedance and painless shock impedance and performs P/R-wave amplitude measurements in all available channels. In the RA and RV the pulse width must be 0.4 ms, in the LV any pulse width can be chosen. For patients in **group A** measurement of all LV pacing vectors is **mandatory** prior to programming of the MPP feature, either after implantation or at time of Pre-hospital discharge. Pacing polarities of the LV

channel must be documented. For patients of **group B**, only measurement of the right channel is required (in DX leads also sensing measurements in the atrial channel).

In group A and B the appropriate sensing and pacing should be evaluated at the 3-month follow-up. In **group A** evaluation should be done in all available channel. In **group B** only the RV channel has to be assessed, for DX leads additionally also the atrial sensing. For the evaluation it is necessary to record 10 consecutive intrinsic beats and 10 consecutive pulses with markers on the IEGM, respectively. The "freeze" button needs to be pressed to store the IEGM electronically. The sensing of the lead will be assessed as "adequate" (= the device sensed the current rhythm correctly) or inadequate. In the ventricles the additional option "no intrinsic rhythm" (= patient is fully paced) is available to describe if an evaluation of sensing is not possible. In case the sensing is considered inadequate, the reason "oversensing", "undersensing", "not measurable" (= quality/content of IEGM does not allow any discrimination if senses are correct (e.g. lead dislodgement)) or "other" will be determined. The pacing of the lead will be assessed as adequate (=successful stimulation) or inadequate. In case the pacing is considered inadequate, the reason for the evaluation is required. Possible options are "non-capture" (= no evidence of depolarization after pacing), "no output" (= failure to pace: impulses are generated by the device but is not transferred to the myocardium), "not measurable" (= quality/content of IEGM does not allow any discrimination if stimulation is successful) or "other".

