6. Report all adverse events. In case of a serious adverse event, or adverse device effect (ADE), please provide the information immediately to BIOTRONIK, and inform the ethical committee, if required. Report adverse events within the indicated timelines (see section 18.9). If the Ilivia ICD or Plexa ICD lead is exchanged or repositioned the follow-up schedule is adapted as described in section 9.8 "Interim Intervention". Report adverse events within the indicated timelines (see section 18.9).

9.5 3-month follow-up

Three months (\pm 30 days) after the implant procedure, the patient has to return to the hospital for assessment of the implanted system. The investigator reviews the system performance and adjusts the programmed parameters as necessary to optimize the ICD functions. The requirements of this procedure are listed below:

1. Reprogramm ICD settings as applicable to optimize ICD/CRT-D functions
2. The following data have to be measured at the end of the follow-up (same as during implantation) with the final programmed ICD settings:
 - Pacing thresholds measured manually or triggered automatically in all channels (**group A**) or RV only (**group B**). For patients in **group A** with MPP activated, both LV vectors have to be measured accordingly. In all channels the pulse width must be 0.4 ms.
 - P/R-wave sensing amplitude (mean value) of all channels (or RV lead only (**group B**)), including also atrial sensing amplitude in DX leads.

- Pacing impedance of all channels (or RV lead only (**group B**)). For the LV channel, measurement of the pacing threshold automatically also provides impedance measurement values.
 - Painless shock impedance
 - Pacing polarities of the LV channel (CRT-D devices only (**group A**))
 - Evaluate the system performance at end of follow-up for all channels (**group A**) or the RV channel and for DX lead also atrial sensing channel (**group B**). It is recommended to record 10 consecutive intrinsic beats (sensing test) and 10 consecutive pulses (threshold test) with markers on the IEGM. Press the "freeze" button to store the IEGM electronically.
3. Document device statistics for CRT-D patients (CRT-D patients only).
 4. Document changes in programming of MPP settings, if applicable (**group A**, CRT-D patients only).

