Data file, identifier_patient_display_id_full	Descriptive	Variable name	Variable label, NEW prefix added to all labels "Implantation device data, second LV pacing vector: "	Variable level	Nominal values
implantation_device_data	No	imp_lv_first_pvect	Programmed first LV pacing vector	nominal	[...]
implantation_device_data	No	imp_lv_sec_pvect	Programmed second LV pacing vector	nominal	[...]
data_SAR	Yes	imp_lv_first_sec_pvect_SAR ⁴⁹	Programmed first and second LV pacing vector	nominal	#

There are 132 possible vector combinations. All vector combinations used in the study have to be reported in the SAR, whereby the most frequent vector combination has to be reported in the CIR, only.

The CIP suggests using 0.4 ms pulse width for all LV threshold measurements, but other values were permitted. In the SAP version 1.0 it has been defined that it will be tested during blind review whether a meaningful number of measurements were performed with another pulse duration than 0.4 ms.

This test showed that very few or no LV threshold measurements used other values than 0.4 ms at implantation.

Therefore, **thresholds of device measurements will be reported for 0.4 ms pulse duration** only and measurements at other pulse duration will be discarded.

⁴⁷ IF imp_lv_first_pulse = 0.4, THEN imp_lv_first_thresh_04 = imp_lv_first_thresh

⁴⁸ IF imp_lv_sec_pulse = 0.4, THEN imp_lv_sec_thresh_04 = imp_lv_sec_thresh

⁴⁹ imp_lv_first_sec_pvect_SAR = combination of imp_lv_first_pvect and imp_lv_sec_pvect per patient

Implantation Device Data / LV / Programmed Pacing Vectors / Not-measured

Data file, identifier_patient_display_id_full	Descriptive	Variable name	Variable label	Variable level	Nominal values
implantation_device_data	No	imp_lv_first_imp_no	-	nominal	Out of range >3000 Out of range <200 Not measurable: no overpacing possible Not done
data_SAR	Yes	imp_lv_first_imp_no_SAR ⁵⁰	Implantation device data, first LV pacing vector: Pacing impedance	nominal	Out of range Measured
implantation_device_data	No	imp_lv_first_thresh_no	-	nominal	No capture with 7.5V possible Not measurable: no overpacing possible Not done
data_SAR	Yes	imp_lv_first_thresh_no_SAR ⁵¹	Implantation device data, first LV pacing vector: Pacing threshold	nominal	No capture with 7.5V possible Measured

Data file, identifier_patient_display_id_full	Descriptive	Variable name	Variable label	Variable level	Nominal values

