Here, the CIP does not suggest a specific pulse duration.

In the SAP version 1.0 it has been defined that it will be tested during blind review whether a meaningful number of measurements were performed with another pulse duration than 0.4 ms.

This test showed that most threshold measurements were done with 0.4 ms, but a number were done with 1.0 or 1.5 ms. These will be reported additionally to those at 0.4 ms, because long pulse durations indicate that the threshold was high at shorter pulse durations.

Thresholds of 1.0 and 1.5 ms duration will be summarized because the thresholds at these durations are similar.

The above analyses are performed for the following 12 vector permutations, respectively:

- 01 LV1 tip to LV2 ring
- 02 LV1 tip to LV4 ring
- 03 LV1 tip to RV coil
- 04 LV1 tip to ICD
- 05 LV2 ring to LV1 tip
- 06 LV2 ring to LV4 ring
- 07 LV2 ring to RV coil
- 08 LV3 ring to LV2 ring
- 09 LV3 ring to LV4 ring
- 10 LV3 ring to RV coil
- 11 LV4 ring to LV2 ring
- 12 LV4 ring to RV coil

⁵⁷ IF mpp_lv_pulse_01 = 0.4, THEN mpp_lv_thresh_01_04 = mpp_lv_thresh_01

⁵⁸ IF mpp_lv_pulse_01 = 1.0 OR 1.5, THEN mpp_lv_thresh_01_15 = mpp_lv_thresh_01

Multipole Pacing / LV / 12 Pacing Vectors / Not-measured

Data file, identifier <small>patient_</small> <small>display_id_full</small>	Descriptive	Variable name	Variable label, NEW prefix added to all labels	Variable level	Nominal values
Multipole_pacing	No	mpp_lv_imp_01_no	-	nominal	Out of range > 3000 out of range < 200 Not done
data_SAR	Yes	mpp_lv_imp_01_no SAR ⁵⁹	Multipole pacing data, LV1 tip to LV2 ring: Pacing impedance	nominal	Out of range Measured
Multipole_pacing	No	mpp_lv_thresh_01_no	-	nominal	True / False
data_SAR	Yes	mpp_lv_thresh_01_no_SAR ⁶⁰	Multipole pacing data, LV1 tip to LV2 ring: Pacing threshold	nominal	No capture with 7.5 V possible Measured
Multipole_pacing	Yes	mpp_lv_pns_01	Phrenic nerve stimulation detected	nominal	Yes / No

The above analyzes are performed for all 12 vector permutations, respectively.

Multipole Pacing / LV / Programmed Delay

Data file, identifier <small>patient_</small> <small>display_id_full</small>	Descriptive	Variable name	Variable label, NEW prefix added to all "Multipole pacing data: "	Variable level	Nominal values
Multipole_pacing	Yes	mpp_lvlv_delay_reason	NEW: Main reason for choice of delay LV-LV	nominal	According to recommended [...] Standard setting used Best hemodynamic response [...] Other

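### LV thresholds not taken at 0.4 ms are dropped at PHD, 3 and 6 months without a reported check for those visits, so the descriptive LV threshold summaries risk being biased low

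*SAP*

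**What the plan says.** **SAP, discard rule.** Section 11.2 (PHD) states for the first and second programmed LV vectors: "As threshold measurements at other pulse durations than 0.4 will be discarded". It justifies this only by pointing back to 10.2. Section 13.2 (3 months) defines its LV programmed-vector variables by reference to 11.2, and 14.2 (6 months) by reference to 13.2.

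**SAP, evidence for the rule.** Section 10.2 reads the protocol as permissive: "The CIP suggests using 0.4 ms pulse width for all LV threshold measurements, but other values were permitted". It then reports the blind review: "This test showed that very few or no LV threshold measurements used other values than 0.4 ms at implantation". From this it concludes that device thresholds are reported at 0.4 ms "only and measurements at other pulse duration will be discarded".

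**SAP, a different rule for similar data.** Section 12.2 covers the 12-vector measurements made when MultiPole Pacing (MPP) is programmed. There the review found: "This test showed that most threshold measurements were done with 0.4 ms, but a number were done with 1.0 or 1.5 ms". Those values are kept and reported in addition, "because long pulse durations indicate that the threshold was high at shorter pulse durations".

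**Protocol.** Section 8.5.11, which covers the end of implantation and of each follow-up, fixes 0.4 ms for RA and RV but says "in the LV any pulse width can be chosen". Section 9.5 (3-month visit) says "In all channels the pulse width must be 0.4 ms". Section 9.4 (PHD) and section 9.6 (6 months) take their measurement procedure from 9.5.

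**The concern.** When a value is dropped because of the pulse width used, and the pulse width was lengthened because the threshold was high, the missingness depends on the value itself. That is the SAP's own reasoning in 12.2, and it gives no reason why the reasoning should stop at the programmed vectors.

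The discard may be harmless where few values are affected, which is what 10.2 reports for implantation. For PHD, 3 and 6 months the SAP cites no LV result, yet the same rule applies. The protocol gives sites two different instructions for these visits, so values away from 0.4 ms can arise without any departure from 8.5.11.

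What is at stake is descriptive. The study is meant to find residual risks, mean lead measurements at each follow-up are planned outputs (protocol 8.4.1), and a rise in capture threshold is among the expected MPP events (protocol Table 8e). A follow-up table that may omit some of the highest LV thresholds, without saying how many, is weaker for that purpose.

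**Working it through.** The documents give no figure for this point, so there is none to reproduce. The check compares the sections and then sizes the possible bias under stated assumptions.

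**1. Which rule and which evidence apply at each visit (LV device thresholds, programmed vectors)**

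| Visit | Protocol on LV pulse width | SAP rule | LV blind-review result cited |
|---|---|---|---|
| Implantation | free (8.5.11 and 9.3 agree) | 0.4 ms only (10.2) | yes, very few or none off 0.4 ms |
| PHD | free (8.5.11) or 0.4 ms (9.4 via 9.5) | 0.4 ms only (11.2) | none |
| 3 months | free (8.5.11) or 0.4 ms (9.5) | 0.4 ms only (13.2 via 11.2) | none |
| 6 months | free (8.5.11) or 0.4 ms (9.6 via 9.5) | 0.4 ms only (14.2 via 13.2) | none |

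The contradiction and the missing check fall on the same three visits. Implantation has neither problem.

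**2. Would the output show the loss?**

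- The raw PHD fields `phd_lv_first_thresh_no` and `phd_lv_sec_thresh_no` do have an option for a threshold not measured at 0.4 ms (SAP 11.2).
- The derived `_SAR` status variable, inherited from 10.2, has only two levels: no capture at 7.5 V, and measured. The raw option is not carried forward.
- The measured level is set whenever the general threshold variable is non-missing, with no condition on pulse width. SAP 11.2 calls that same variable unnecessary for the analysis. The status is therefore not tied to a 0.4 ms value.
- The standard table for continuous data prints a missing count (SAP 5.1). As written, these analyses use the whole Ilivia analysis set, in which 26 + 26 = 52 of the 105 planned patients have single- or dual-chamber devices. The count also mixes in missed visits and tests not done, so it cannot isolate the discarded values.

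**3. Possible size**

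Let f be the share of LV thresholds discarded, m_k the mean of the kept values, and m_d the mean that the discarded patients would have had at 0.4 ms.

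- Full mean = (1 − f) × m_k + f × m_d
- Reported mean = m_k
- Bias = reported − full = −f × (m_d − m_k)

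The documents give neither f nor the gap m_d − m_k, so both are assumed. The only document input is the 53 planned CRT-D patients (protocol 8.8.1).

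| f (patients of 53) | gap 0 V | gap 1 V | gap 2 V | gap 3 V |
|---|---|---|---|---|
| 0 (0) | 0 | 0 | 0 | 0 |
| 1/53 (1) | 0 | −0.02 V | −0.04 V | −0.06 V |
| 5% (2.7) | 0 | −0.05 V | −0.10 V | −0.15 V |
| 9% (4.8) | 0 | −0.09 V | −0.18 V | −0.27 V |
| 18% (9.5) | 0 | −0.18 V | −0.36 V | −0.54 V |

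For example, 0.09 × 2 = 0.18 V. The sign is negative whenever discarded patients have the higher 0.4 ms thresholds, which is what the reasoning in 12.2 implies for long pulses.

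**The case against.** The strongest reply is that no follow-up value is shown to be lost. The visit procedure in protocol 9.5 asks for 0.4 ms, and SAP 11.2 is written on that footing. If sites followed 9.5, nothing is discarded. This stands, and it limits the point to a risk. A reader might infer that the follow-up summaries are in fact biased low, but the documents give no count of affected values and do not support that.

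Second, a width other than 0.4 ms need not be a long one. For the analyzer data the common alternative was 0.5 ms, which the SAP links to analyzers' standard settings. This also stands: the gap could be near zero.

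Third, 10.2 and 12.2 apply the same test, namely whether a meaningful number of values used another width, and differ because the results differed. The data differ too: 12.2 covers all 12 vectors, including ones never programmed, whereas the programmed vectors are chosen partly for a low threshold. This explains the difference at implantation. It does not supply a result for PHD, 3 or 6 months.

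Fourth, high thresholds show up elsewhere: the longer-pulse rows of the MPP tables, the no-capture status, and high LV threshold as a tabulated reason for changing a vector. This is partly right, but the MPP form records programming at implant or PHD, not the thresholds measured at 3 and 6 months.

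Three further inferences should be resisted. Implantation data are not implicated, since the protocol is consistent there and the review found almost nothing to drop. The data collection form does not lack the option for a threshold not measured at 0.4 ms; only the derived variable does. No understated share of patients above 2.5 V can be claimed, because the SAP plans no such output.

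**Conclusion.** The point holds as a minor reporting gap at PHD, 3 and 6 months. The SAP extends a discard rule to visits for which it reports no LV check, against reasoning that it accepts in 12.2, and under a protocol that gives sites conflicting instructions. The LV threshold summaries at those visits are therefore at risk of being biased low.

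The size is unknown. It is zero if all values were taken at 0.4 ms or if pulse width is unrelated to threshold. Over the assumed range it runs from about 0.02 V to about 0.5 V in the mean. These figures are illustrations and not estimates.

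The summaries are descriptive, with no hypothesis attached. Neither primary endpoint, none of the secondary endpoints, and neither sample size depends on them.

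**What to change.** In SAP 11.2, 13.2 and 14.2, for the programmed LV vectors:

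- Report at each visit the number of thresholds at 0.4 ms, the number at other widths, and the number flagged as not measured at 0.4 ms.
- Carry that flag into the derived `_SAR` status variable, and set the measured level only from a 0.4 ms value.
- Show any recorded longer-pulse LV thresholds in a separate row, as 12.2 does, without pooling them with 0.4 ms values.
- State the blind-review result for PHD, 3 and 6 months. If no values were affected, one sentence closes the point.

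Protocol 8.5.11 and 9.5 (with 9.4 and 9.6) must be reconciled on the LV pulse width; this review takes no position on which instruction should stand. Rewording will not change measurements already made, which is why the counts matter.

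The cost is a few extra table rows, a small change to the derivation footnotes, and a wording correction in the protocol.

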11.3. Treatment of Missing and Spurious Data

See general definitions in chapter 5.4.

11.4. Exclusion of Particular Information

See general definitions in chapter 5.5.

11.5. Descriptive Analyses

See general definitions in chapter 5.1.

11.6. Hypotheses & Statistical Tests

There are no pre-defined statistical hypotheses.

12. Multipole Pacing Data: Ilivia

12.1. Analysis set

All analyses are performed for the Ilivia analysis set⁵⁵.

12.2. Variables

Multipole Pacing / General Information

Data file, identifier patient_ display_id_full	Descriptive	Variable name	Variable label, NEW prefix added to all labels "Multipole pacing data: "	Variable level	Nominal values
Multipole_pacing	No	mpp_visdate	Date of MPP programming	date	n.a.
Multipole_pacing	Yes	mpp_visit	Final programming of MPP has been done	nominal	At implant At Pre-hospital discharge Not done Other
Multipole_pacing	Reporting for each patient if the above variable = other	mpp_visit_co	[NEW] Multipole pacing data: Comments related to final programming	text	...
phd_device_data	Yes	phd_lv_first_vect_no	no LV pacing programmed	nominal	True / False
phd_device_data	Yes	phd_lv_sec_vect_no	no second vector programmed, MPP inactive	nominal	True / False
fu_3_month_device_data	Yes	fu3_lv_first_vect_no	no LV pacing programmed	nominal	True / False
fu_3_month_device_data	Yes	fu3_lv_sec_vect_no	no second vector programmed, MPP inactive	nominal	True / False
fu_6_month_device_data	Yes	fu6_lv_first_vect_no	no LV pacing programmed	nominal	True / False
fu_6_month_device_data	Yes	fu6_lv_sec_vect_no	no second vector programmed, MPP inactive	nominal	True / False

A list of all patients with True for one of the "no LV pacing / second vector programmed" variables, together with general comments for the respective follow-up, will be presented.

⁵⁵ analysis_set_Ilivia_SAR = Yes

Multipole Pacing / LV / Programmed Sensing Vector

Data file, identifier patient_ display_id_full	Descriptive	Variable name	Variable label, NEW prefix added to all labels "Multipole pacing data: "	Variable level	Nominal values
Multipole_pacing	Yes	mpp_lv_svect	Permanent programmed sensing vector	nominal	LV1 tip to LV2 ring [...]
Multipole_pacing	Yes	mpp_lv_svect_reason	Main reason for vector choice	nominal	Highest amplitude [...] Best signal quality [...] Most appropriate [...] Standard use of vector Other
Multipole_pacing	Reporting for each patient if the above variable = other	mpp_lv_svect_reason_co	[NEW] Multipole pacing data: Comments related to reason for vector choice	text	...

Multipole Pacing / LV / Programmed Pacing Vectors

Data file, identifier patient_ display_id_full	Descriptive	Variable name	Variable label, NEW prefix added to all labels "Multipole pacing data, first LV pacing vector: "	Variable level	Nominal values
Multipole_pacing	Yes	mpp_lv_first_pvect	Programmed first LV pacing vector	nominal	LV1 tip to LV2 ring [...]
Multipole_pacing	Yes	mpp_lv_first_reason	Main reason for vector choice	nominal	According to clinical routine Lowest available threshold To prevent phrenic nerve stimulation Best anatomical position Best available threshold [...] According to recommended [...] Other
Multipole_pacing	Reporting for each pt. if the above variable = other	mpp_lv_first_reason_co	[NEW] Multipole pacing data: Comments related to programmed first vector	text	...

Data file, identifier patient_ display_id_full	Descriptive	Variable name	Variable label, NEW prefix added to all labels "Multipole pacing data, second LV pacing vector: "	Variable level	Nominal values
Multipole_pacing	Yes	mpp_lv_sec_pvect	Programmed second LV pacing vector	nominal	[...]
Multipole_pacing	Yes	mpp_lv_sec_reason	Main reason for vector choice	nominal	According to clinical routine Lowest available threshold To prevent phrenic nerve stimulation Best anatomical position Best available threshold [...] According to recommended [...] Other
Multipole_pacing	Reporting for each pt. if the above variable = other	mpp_lv_sec_reason_co	[NEW] Multipole pacing data: Comments related to programmed second vector	text	...
data_SAR	Yes	mpp_lv_first_sec_pvect_SAR ⁵⁶	Programmed first and second LV pacing vector	nominal	#

A large number of combinations of vector pairs for MPP is possible. Only the most frequent combinations will be reported.
Combinations of two vectors for MPP in which only the designation as "first" and "second" are exchanged will be reported as one.

⁵⁶ mpp_lv_first_sec_pvect_SAR = combination of mpp_lv_first_pvect and mpp_lv_sec_pvect per patient

Multipole Pacing / LV / 12 Pacing Vectors

Data file, identifier_patient_display_id_full	Descriptive	Variable name	Variable label, NEW prefix added to all labels "Multipole pacing data, [specification ... to ...]: "	Variable level	Nominal values
Multipole_pacing	Yes	mpp_lv_imp_01	Pacing impedance [Ω]	scale	n.a.
Multipole_pacing	No	mpp_lv_thresh_01	Pacing threshold [V]	scale	n.a.
Multipole_pacing	No	mpp_lv_pulse_01	at Pulse width [ms]	scale	n.a.
data_SAR	Yes	mpp_lv_thresh_01_04 ⁵⁷	Pacing threshold [V] at 0.4 ms	scale	n.a.
data_SAR	Yes	mpp_lv_thresh_01_15 ⁵⁸	Pacing threshold [V] at 1.0 or 1.5 ms	scale	n.a.
Multipole_pacing	Yes	mpp_lv_pns_amp_01	Phrenic nerve stimulation at pacing amplitude [V]	scale	n.a.

A pacing threshold must always consist of amplitude and duration (pulse width). It is not reasonable to report one without the other.

Here, the CIP does not suggest a specific pulse duration.

In the SAP version 1.0 it has been defined that it will be tested during blind review whether a meaningful number of measurements were performed with another pulse duration than 0.4 ms.

This test showed that most threshold measurements were done with 0.4 ms, but a number were done with 1.0 or 1.5 ms. These will be reported additionally to those at 0.4 ms, because long pulse durations indicate that the threshold was high at shorter pulse durations.

Thresholds of 1.0 and 1.5 ms duration will be summarized because the thresholds at these durations are similar.

The above analyses are performed for the following 12 vector permutations, respectively:

- 01 LV1 tip to LV2 ring
- 02 LV1 tip to LV4 ring
- 03 LV1 tip to RV coil
- 04 LV1 tip to ICD
- 05 LV2 ring to LV1 tip
- 06 LV2 ring to LV4 ring
- 07 LV2 ring to RV coil
- 08 LV3 ring to LV2 ring
- 09 LV3 ring to LV4 ring
- 10 LV3 ring to RV coil
- 11 LV4 ring to LV2 ring
- 12 LV4 ring to RV coil

⁵⁷ IF mpp_lv_pulse_01 = 0.4, THEN mpp_lv_thresh_01_04 = mpp_lv_thresh_01

⁵⁸ IF mpp_lv_pulse_01 = 1.0 OR 1.5, THEN mpp_lv_thresh_01_15 = mpp_lv_thresh_01

Multipole Pacing / LV / 12 Pacing Vectors / Not-measured

Data file, identifier <small>patient_</small> <small>display_id_full</small>	Descriptive	Variable name	Variable label, NEW prefix added to all labels	Variable level	Nominal values
Multipole_pacing	No	mpp_lv_imp_01_no	-	nominal	Out of range > 3000 out of range < 200 Not done
data_SAR	Yes	mpp_lv_imp_01_no SAR ⁵⁹	Multipole pacing data, LV1 tip to LV2 ring: Pacing impedance	nominal	Out of range Measured
Multipole_pacing	No	mpp_lv_thresh_01_no	-	nominal	True / False
data_SAR	Yes	mpp_lv_thresh_01_no_SAR ⁶⁰	Multipole pacing data, LV1 tip to LV2 ring: Pacing threshold	nominal	No capture with 7.5 V possible Measured
Multipole_pacing	Yes	mpp_lv_pns_01	Phrenic nerve stimulation detected	nominal	Yes / No

The above analyzes are performed for all 12 vector permutations, respectively.

Multipole Pacing / LV / Programmed Delay

Data file, identifier <small>patient_</small> <small>display_id_full</small>	Descriptive	Variable name	Variable label, NEW prefix added to all "Multipole pacing data: "	Variable level	Nominal values
Multipole_pacing	Yes	mpp_lvlv_delay_reason	NEW: Main reason for choice of delay LV-LV	nominal	According to recommended [...] Standard setting used Best hemodynamic response [...] Other
Multipole_pacing	Yes	mpp_rvlv_delay_reason	NEW: Main reason for choice of delay RV-LV	nominal	According to recommended [...] Standard setting used Best hemodynamic response [...] Other
Multipole_pacing	Yes	mpp_order_rvlv	Pacing order	nominal	RV first LV first
Multipole_pacing	Yes, for the above groups "RV first" and "LV first"	mpp_lvlv_delay	LV-LV delay [ms]	scale	n.a.
Multipole_pacing	Yes, for the above groups "RV first" and "LV first"	mpp_rvlv_delay	RV-LV delay [ms]	scale	n.a.

⁵⁹ IF mpp_lv_imp_01_no = ... > 3000 OR
mpp_lv_imp_01_no = ... < 200 THEN mpp_lv_imp_01_no_SAR = Out of range
ELSE IF mpp_lv_imp_01 ≠ missing THEN mpp_lv_imp_01_no_SAR = Measured

⁶⁰ IF mpp_lv_thresh_01_no = True THEN mpp_lv_thres_01_no_SAR= No capture ...
ELSE IF mpp_lv_thresh_01 ≠ missing THEN mpp_lv_thres_01_no_SAR = Measured

Multipole Pacing / LV /Handling Evaluation

Data file, identifier patient_ display_id_full	Descriptive	Variable name	Variable label, NEW prefix added to all "Multipole pacing data: "	Variable level	Nominal values
Multipole_pacing	Yes	mpp_handling_activation	Activation of MPP	nominal	Very easy.... Easy.... Moderate.... Moderate-difficult... Difficult
Multipole_pacing	Yes	mpp_handling_navigation	Navigation to MPP programming from the parameter page	nominal	
Multipole_pacing	Yes	mpp_handling_lvlv	Programming of LV-LV delay	nominal	
Multipole_pacing	Yes	mpp_handling_rvlv	Programming of RV-LV delay	nominal	
Multipole_pacing	Yes	mpp_handling_overall	Overall handling of MPP programmer interface	nominal	
data_SAR	Yes	mpp_handling_activation_SAR ⁶¹	Activation of MPP	ordinal	
data_SAR	Yes	mpp_handling_navigation_SAR ⁶²	Navigation to MPP programming from the parameter page	ordinal	
data_SAR	Yes	mpp_handling_lvlv_SAR ⁶³	Programming of LV-LV delay	ordinal	
data_SAR	Yes	mpp_handling_rvlv_SAR ⁶⁴	Programming of RV-LV delay	ordinal	
data_SAR	Yes	mpp_handling_overall_SAR ⁶⁵	Overall handling of MPP programmer interface	ordinal	

⁶¹ IF mpp_handling_activation = Very easy....
 ELSE IF mpp_handling_activation = Easy....
 ELSE IF mpp_handling_activation = Moderate....
 ELSE IF mpp_handling_activation = Moderate-difficult...
 ELSE IF mpp_handling_activation = Difficult

THEN mpp_handling_activation = 1
 THEN mpp_handling_activation = 2
 THEN mpp_handling_activation = 3
 THEN mpp_handling_activation = 4
 THEN mpp_handling_activation = 5

⁶² see above

⁶³ see above

⁶⁴ see above

⁶⁵ see above

Multipole Pacing / LV / Handling Information

Data file, identifier patient_ display_id_full	Des cript ive	Variable name	Variable label, NEW prefix added to all "Multipole pacing data: "	Varia ble level	Nominal values
Multipole_ pacing	Yes	mpp_time_program	At which point in time would you program MPP in a regular CRT-D patient (independent from study set-up)	nomi nal	After implantation Prior to 6 -month FU At 6 -month FU After 6 -month FU Not at all Other
Multipole_ pacing	Yes	mpp_pat_program	In which patients would you programm MPP ? (independent from study participation)	nomi nal	Responder to conventional CRT Non-responder to conventional CRT All CRT patients
Multipole_ pacing	Yes	mpp_info_sufficient	Did you measure several available vectors during implantation via external analyzer to ensure that sufficient vectors are available due to lead positioning ?	nomi nal	Yes / No
Multipole_ pacing		mpp_info_sufficient	Was the information sufficient to find suitable vectors for programming later ?	nomi nal	Yes / No
Multipole_ pacing	Yes	mpp_vect_suitable	Were suitable vectors available for final programming ?	nomi nal	Yes / No

